### **13.0 Statistical Analysis**

#### **13.1 Overview of Statistical Analyses**

Prior to conducting the primary or secondary analyses, descriptive statistics (i.e., frequencies, measures of central tendency) will characterize the sample in terms of important socio-demographic and clinical characteristics (e.g., age, education, race/ethnicity, and menopausal status) and any other relevant covariates. All outcome variables will be assessed for normality and, if necessary, normalizing transformations may be applied or change scores may be used for outcome measures in analyses. We will describe the interrelationships between all outcomes (primary and secondary) by calculating correlations. To determine whether the enrolled sample differs from eligible study refusers, we will compare these groups on key socio-demographic and clinical factors obtained during screening (e.g., age, treatments) and on severity of sexual concerns using two-sample t-tests or Chi-square tests. Any variables with significant imbalance will be entered in our between groups analyses as covariates. Study completers will also be compared to non-completers on these variables. Every effort will be made to minimize couple drop-out, although some degree of attrition is expected. Logistic regression will be used to understand what factors are predictive of drop-out at the participant level. Factors for possible inclusion in this model include intervention arm, age, level of pre-treatment patient sexual function, and interactions involving intervention arm. Reasons for drop-out will be queried, categorized, and compared within each intervention arm. Our main analyses will account for missing data using multiple imputation with chained equations (MICE). This method will provide valid inferences provided that the probability of having missing data (i.e. drop-out) only depends on the observed data (e.g. treatment arm, baseline sexual function). We chose MICE because it can be used with multi-level models, and it has the ability to readily accommodate categorical variables.

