#### 4.3 Overview of Randomization and Intervention Conditions

Couples will be randomized with an allocation ratio of 1:1 to either the IE or the Educational Control (Living Healthy Together) condition with stratification by age at diagnosis ( $\leq 45$  vs.  $> 45$ ) using the age obtained from the medical record (or by the patient during screening, if age at diagnosis is not available in the medical record). The statistician ([name]) will generate the randomization sequences using an automated randomization procedure in REDCap that limits prediction of allocation and protects masking of allocations. Randomization in blocks of four will guarantee that after every four assignments the study arms will have equal numbers. Separate randomization tables will be used for FCCC, Duke, and community participants to minimize the potential for unequal randomization by site.

Randomization will occur once both members of the couple have consented, completed baseline surveys, and are scheduled for their first intervention session. Randomization will occur centrally at the primary site by a staff member uninvolved in recruitment (to reduce the potential for bias in randomizing participants onto certain conditions). Once randomized, the couple will be sent sealed study materials along with the instructions to leave the envelopes sealed until they “meet” with their interventionist for session 1. It is important to keep the study condition a secret from participants until Session 1 to reduce the chances for unequal drop-out prior to Session 1, which could occur if patients/partners are more motivated to attend sessions in one study group as opposed to the other.

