### **13.2 Statistical Analyses for Aim 1 (Primary Aim; Effects of IE Intervention on Patient Sexual Function)**

The primary analysis will examine whether, relative to the LHT condition, the IE condition leads to greater increases in the primary outcome of patient sexual function at all three post-treatment assessments (T2-4; post-treatment; 3-month FU; 6-month FU). We will also examine specific domains of sexual function (satisfaction, desire, arousal, lubrication, orgasm, pain) separately. In a mixed effects regression model, study condition will serve as the independent variable and patient sexual function at each time point will serve as the dependent variable; pre-treatment sexual function will be included in the model as a covariate with time included as a categorical covariate. Intervention by time interaction effects will be included to test the intervention effect at each follow-up time. Subject-specific random intercepts will account for within-subject variability. Intervention effects on patient sexual function at each follow-up are tested using F tests of combined main and interaction effects.

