### **13.6 Statistical Analyses for Exploratory Aim 1 (Age and Race/Ethnicity as Intervention Moderators)**

In the primary analysis described above, we will explore (but do not expect to find) interactions between intervention effects and both age ( $\leq 45$  versus  $> 45$ ) and race/ethnicity (White versus non-White). Based

on pilot data, we estimate that approximately 30% and 25% of the sample will be classified as younger or non-White, respectively. Separate models will be fit for the 2 potential moderators. We will add age/race and interactions between the moderator, intervention, and time point in the regression model described in the Primary Aim. If the 3-way interaction between age/race, intervention, and follow-up time is significant, assessed via a likelihood ratio test, this will provide evidence that the treatment effect significantly differs by age or race. However, interaction effects not meeting statistical significance, but with an estimated magnitude  $> (.5 * \text{main effect})$  will suggest sub-threshold subgroup effects that we will consider in planning next steps including tailoring the IE intervention.

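### Covariates for the IE–LHT comparison are chosen by testing enrollees against refusers, while the primary model omits the factors that stratify randomisation

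*Combined protocol and SAP*

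**What the plan says.** Section 13.1 introduces the screen with: "To determine whether the enrolled sample differs from eligible study refusers, we will compare these groups on key socio-demographic and clinical factors". The tests are two-sample t-tests or chi-square tests on screening data, with age, treatments and severity of sexual concerns named. The next sentence is the selection rule: "Any variables with significant imbalance will be entered in our between groups analyses as covariates". No baseline comparison of IE with LHT is described before it. The rule gives no significance threshold and no closed list of variables.

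Section 4.3 randomises couples 1:1 in blocks of four "with stratification by age at diagnosis", at 45 or under versus over 45. It adds: "Separate randomization tables will be used for FCCC, Duke, and community participants to minimize the potential for unequal randomization by site".

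Section 13.2 gives the primary model: condition, time, condition by time, subject random intercepts and the baseline score ("pre-treatment sexual function will be included in the model as a covariate with time included as a categorical covariate"). Neither age group nor recruitment source is listed. Age group enters a model of the primary outcome only for exploratory moderation in section 13.6. Age is also a covariate in the mediation models of section 13.5. Recruitment source is in no model.

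**The concern.** There are two defects, and both affect the primary model.

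First, the covariate rule tests the wrong groups. Refusers are never randomised. A variable on which they differ from enrollees bears on generalisability. It cannot confound a randomised comparison among enrollees, and it may be unrelated to FSFI. If the authors meant imbalance between arms, any such imbalance after randomisation is chance, and selecting on it is data-driven. On either reading the covariates of the primary analysis are not fixed in advance.

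Second, the analysis does not follow the randomisation. Stratified blocks force the arms to be nearly balanced on age group and recruitment source, so variation between strata contributes little to the true variance of the treatment difference. A model without the strata still counts that variation in its residual. Its standard error is then too large and its test conservative whenever the strata predict FSFI. The precision that stratification was meant to buy is discarded.

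**Working it through.** **The plan's own figure.** Section 13.8 gives a 5-point difference, SD of change 8.2, 92 analysable couples (46 per arm), two-sided alpha 0.05 and 82% power.

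- SE = 8.2 × √(2/46) = 1.710, and 5/1.710 = 2.924.
- Normal approximation: Φ(2.924 − 1.960) = 83.3%. Noncentral t with 90 df: 82.5%. The stated 82% reproduces.

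**Residual SD for a baseline-adjusted model.** Section 13.8 also gives an SD of about 10. Assuming equal variances at both times, 8.2² = 2 × 10² × (1 − ρ), so ρ = 0.664. The residual SD is 10 × √(1 − 0.664²) = 7.48. This is why the power figures in the first table exceed 82%.

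**Size of the effect by formula.** Let R² be the share of residual variance explained by the strata. With balance on the strata, omitting them inflates the SE by 1/√(1 − R²): 1.026, 1.054 and 1.085 at R² = 0.05, 0.10 and 0.15. The three degrees of freedom spent on adjustment take back a little of this.

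**Simulation.** 92 couples, blocks of four within six strata (two age groups by three lists), 30% in the younger group (section 13.6), one follow-up time. The list shares of 45/45/10%, additive stratum effects and R² are assumptions. The rows for R² of 0.05 to 0.15 use 4,000 trials each.

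Residual SD 7.48:

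| R² | SE overstated | Type I error, omitted / included | Power at 5 points, omitted / included |
|---|---|---|---|
| 0 | – | 0.049 / 0.049 | 0.891 / 0.888 |
| 0.05 | 2.4% | 0.045 / 0.051 | 0.890 / 0.899 |
| 0.10 | 5.3% | 0.041 / 0.051 | 0.901 / 0.919 |
| 0.15 | 8.4% | 0.034 / 0.051 | 0.892 / 0.922 |

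Repeat runs gave type I error with the strata omitted of 0.045–0.048, 0.039–0.041 and 0.033–0.037 in the last three rows. The Monte Carlo standard error of a 0.05 rate over 4,000 trials is √(0.05 × 0.95/4000) = 0.003.

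Using the plan's SD of 8.2 as the total (8,000 trials per setting):

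| R² | Type I error, omitted / included | Power, omitted / included |
|---|---|---|
| 0 | 4.8% / 4.9% | 82.8% / 82.4% |
| 0.05 | 4.7% / 5.1% | 83.2% / 84.4% |
| 0.10 | 4.0% / 4.9% | 83.8% / 86.1% |
| 0.20 | 3.1% / 5.2% | 84.1% / 89.0% |

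Dropout does not change the picture. Randomising 120 couples and losing 28 at random gave type I error of 0.044 omitted and 0.054 included at R² = 0.10.

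**How open the covariate set is.** If k independent variables with no true difference are each screened at 0.05 (both assumed), the chance that at least one enters is 1 − 0.95^k: 14% for k = 3, 23% for k = 5 and 34% for k = 8. This is the chance that the primary model changes by luck. It is not an error rate for the treatment effect.

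**The case against.** The strongest reply is that neither defect threatens validity. The refuser screen uses screening data, not arm or outcome, so a covariate chosen that way does not bias IE versus LHT and costs about one degree of freedom. That is correct, and no bias is claimed. What remains is a primary model whose terms depend on an irrelevant comparison.

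The sentence may also simply be misplaced, since imbalance usually refers to arms. That is plausible, but the text does not say so, and selection by significance test would still leave the model open. Analysis with condition masked (section 16.1) limits deliberate steering but does not fix the terms.

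Age could enter through the screen, because section 13.1 names it. That would be contingent, and not necessarily as the 45-year grouping; recruitment source is not named there. Section 4.3 uses the word stratification only for age, but separate tables make source a stratifier in effect.

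Finally, baseline FSFI may already absorb most of any age or source association, leaving R² near zero. This point stands: the gain then disappears (the R² = 0 rows). Even with the strata omitted, simulated power is no lower than the planned 82%.

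**Conclusion.** The concern holds. As written, covariates for the efficacy comparison are selected from a contrast that says nothing about the randomised arms, and the primary model leaves out both factors that structure the randomisation.

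The consequence is modest: an unfixed covariate set, a test that is conservative when the strata matter, and lost precision. The power cost runs from nil at R² = 0 to about 3 points at 0.15, and about 5 points at 0.20. These sizes rest on assumed values of R² and list shares, and on a single-time-point simplification of the repeated-measures model. Type I error is not inflated and the sample size need not change. The correction is still worth making, because it settles the primary model in advance at almost no cost.

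**What to change.** - **Section 13.1:** delete the significant-imbalance rule for efficacy models. Keep the comparison with refusers as description; section 13.7 already plans it.
- **Sections 13.2 to 13.4:** pre-specify as covariates the baseline value of the outcome (unless baseline is itself a modelled time point, which section 13.4 should make clear), the age-at-diagnosis stratum as used at randomisation, and the randomisation list (FCCC, Duke, community).
- **Section 4.2.3.4:** it labels a set of variables as covariates without tying them to a model. State which models, if any, they enter.
- **Multiple imputation:** include the same stratification factors in the imputation model so that it matches the analysis model.

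The cost is wording. Every variable is already collected, and the primary model uses three more degrees of freedom: one for age group and two for list.

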### **13.2 Statistical Analyses for Aim 1 (Primary Aim; Effects of IE Intervention on Patient Sexual Function)**

The primary analysis will examine whether, relative to the LHT condition, the IE condition leads to greater increases in the primary outcome of patient sexual function at all three post-treatment assessments (T2-4; post-treatment; 3-month FU; 6-month FU). We will also examine specific domains of sexual function (satisfaction, desire, arousal, lubrication, orgasm, pain) separately. In a mixed effects regression model, study condition will serve as the independent variable and patient sexual function at each time point will serve as the dependent variable; pre-treatment sexual function will be included in the model as a covariate with time included as a categorical covariate. Intervention by time interaction effects will be included to test the intervention effect at each follow-up time. Subject-specific random intercepts will account for within-subject variability. Intervention effects on patient sexual function at each follow-up are tested using F tests of combined main and interaction effects.

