### **13.8 Power Calculations**

Power calculations are based on Aim 1 (Primary Aim). On the patient sexual function measure, a change of 5 points would be considered clinically meaningful (scale range: 2-36,  $SD \approx 10$ ). Based on pilot data, we anticipate that the  $SD$  of the change scores will be 8.2. Using our prior IE trials to guide attrition estimates, we estimate an attrition rate of 24% at 6-month follow-up, resulting in data available from 92 analyzable couples at 6-month follow-up. We will therefore have 82% power to detect a difference of 5 points in change scores, assuming a 2-sided test with type-I error ( $\alpha$ ) of 0.05. In our breast cancer pilot study, we found a between-groups difference in change scores on patient sexual function of 10.7 at post-treatment. Based on results of similar trials, we expect some attenuation of effects by 6-month follow-up. This study is powered to detect a clinically meaningful change  $> (.5 * \text{main effect})$  through the final assessment point. In sum, the study is conservatively powered to detect an effect of the IE intervention approximately half the size obtained in the pilot trial. The sample size of 120 couples (240 participants) was selected based on these calculations.

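### The primary model names only a random intercept, so under the usual default one pooled variance serves all three follow-up tests, which are miscalibrated if spread changes over follow-up

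*Combined protocol and SAP*

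**What the plan says.** Section 13.2 fits a mixed effects regression to patient FSFI at the three follow-ups (T2 to T4). Baseline FSFI is a covariate, time is categorical and the arm-by-time interaction is included. On covariance it says: "Subject-specific random intercepts will account for within-subject variability". On testing it says: "Intervention effects on patient sexual function at each follow-up are tested using F tests of combined main and interaction effects".

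For Aim 1 no section gives a residual covariance structure, variances by time point, robust standard errors or a degrees-of-freedom method. Section 13.4 does specify extra residual structure, but only for the dyadic Aim 2b models. Section 13.3 carries the Aim 1 model over to partner sexual function (Aim 2a), and section 13.2 also analyses the FSFI domains separately. Section 13.1 plans multiple imputation by chained equations (MICE) for the main analyses.

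Section 13.8 gives an FSFI SD of about 10 and a single change-score SD of 8.2. It sizes the trial on 92 analysable couples at 6 months.

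**The concern.** A random intercept with independent, equal-variance residuals implies the same variance at every follow-up and the same correlation between every pair of follow-ups. Each time-specific test then uses a variance averaged over the three time points. That is harmless if the three variances are equal. If they are not, the standard error is too small where the true variance is above average and too large where it is below.

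Equal variance is not an obvious assumption here. Section 4.4 places the post-treatment survey 2 to 7 days after the last session and the last survey 6 months after it. If baseline FSFI predicts the later score less well, the baseline-adjusted variance rises even when the raw SD stays constant. At stake are the type I error and interval coverage of the individual time-point comparisons, including the 6-month comparison on which the trial is sized. Errors in opposite directions at the two ends of follow-up would also blur any statement about whether the effect lasts.

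**Working it through.** **Inputs from section 13.8.** Difference 5 points, change-score SD 8.2, FSFI SD about 10, two-sided alpha 0.05, 24% attrition, 92 couples at 6 months (46 per arm at the 1:1 allocation of section 4.3).

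**Inputs assumed.** SDs at post-treatment, 3 and 6 months. The documents give none, so a range is shown.

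**Step 1: the plan's own figure.** 120 x 0.76 = 91.2, close to the stated 92. SE = 8.2 x sqrt(2/46) = 1.71, and 5/1.71 = 2.92. Power is Phi(2.92 - 1.96) = 83.3% by the normal approximation and 82.5% by the noncentral t with 90 df. The stated 82% reproduces.

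**Step 2: analytic effect of one pooled variance.** With complete data, the model uses the mean of the three variances at every time point. So

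- SE ratio at time t = sqrt(mean of the three variances) / SD at t
- true alpha at time t = 2 x (1 - Phi(1.96 x SE ratio))

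Example, SDs 8.2/9.0/10.0: mean variance = (67.24 + 81 + 100)/3 = 82.75, so the pooled SD is 9.10. The 6-month ratio is 9.10/10.0 = 0.91, a model SE of 1.90 against a true 2.09. Alpha = 2 x (1 - Phi(1.783)) = 7.5%.

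| Assumed SDs (post / 3 m / 6 m) | 6-month SE ratio | 6-month alpha | Post-treatment alpha |
|---|---|---|---|
| 8.2 / 8.2 / 8.2 | 1.00 | 5.0% | 5.0% |
| 8.2 / 8.6 / 9.0 | 0.96 | 6.1% | 4.0% |
| 8.2 / 9.0 / 10.0 | 0.91 | 7.5% | 3.0% |
| 6.5 / 8.2 / 10.0 | 0.84 | 10.2% | 1.2% |
| 8.2 / 7.8 / 7.4 | 1.06 | 3.9% | 6.2% |

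**Step 3: the same question through the baseline correlation.** If the SD is 10 at both times, a change SD of 8.2 implies r = 1 - 8.2²/(2 x 10²) = 0.664 and an adjusted SD of 10 x sqrt(1 - 0.664²) = 7.48. Assume r falls to 0.58 at 3 months and 0.50 at 6 months. The adjusted SDs are then 7.48, 8.15 and 8.66, the pooled SD is 8.11, the 6-month ratio is 0.936 and alpha is 6.6%.

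**Step 4: simulation of the section 13.2 model.** REML, 120 patients, monotone missingness of about 8%, 16% and 24%, no true effect. Type I error at 6 months:

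| Assumed SDs | Random intercept, available data | Random intercept, multiple imputation | Unstructured, available data |
|---|---|---|---|
| 8.2 / 8.2 / 8.2 | 4.8% | 4.7% | 4.4% |
| 8.2 / 8.6 / 9.0 | 6.5% | 5.7% | 5.1% |
| 8.2 / 9.0 / 10.0 | 6.7% | 5.9% | 4.5% |
| 8.2 / 9.0 / 10.0, autoregressive-type correlation | 7.5% | 6.1% | 4.7% |
| 6.5 / 8.2 / 10.0 | 10.4% | 9.1% | 4.7% |

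Replicates were 3000, 750 and 1500 for the three columns. At a true 5%, the simulation standard errors are about 0.4, 0.8 and 0.6 points. The shrinking case was worked analytically only.

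**The case against.** The strongest reply is that section 13.2 does not say the residuals have constant variance. It is silent, and a residual variance for each time point could be added without contradicting it. That is correct, and it is why the point is about an unspecified structure whose usual default is one variance. The silence still leaves the primary model open, so the structure could be chosen after the data are seen.

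Second, nothing in the documents shows that spread grows. That stands. A reader might infer from section 13.8, "we expect some attenuation of effects by 6-month follow-up", that the plan itself expects it. That sentence concerns the difference in means between arms, which the arm-by-time terms already model, and it says nothing about variance. If spread shrinks, the 6-month test is conservative.

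Third, the planned imputation softens the error. This also stands. Under moderate growth the imputation-based figures of 5.7% to 6.1% cannot be told apart from 5% with 750 replicates.

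Fourth, an error rate near 10% needs an extreme pattern. For example, adjusted SDs of 7.0/7.6/9.6 give 9.6% analytically. With the SD held at 10, they require the baseline correlation to fall from sqrt(1 - 0.49) = 0.71 to sqrt(1 - 0.9216) = 0.28 within six months. Sections 1.0 and 3.0 describe sexual concerns that persist for years, which makes so steep a fall hard to assume.

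**Conclusion.** The point holds as a conditional, cheap improvement. If the baseline-adjusted variance differs across follow-ups and residuals are given one variance, the standard errors and F tests at individual time points are miscalibrated. For moderate growth in spread the 6-month type I error is about 6% to 7.5% without imputation and about 6% with it. It is about 10% only under steep growth and about 3.9% if spread shrinks as assumed above. If the variances are equal, nothing is lost. All these figures rest on assumed SDs by time point.

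Two stronger readings are not supported. One is that the 6-month test is too liberal as planned: the documents fix neither the residual structure nor the direction of any change in spread. The other is that the power statement fails: "We will therefore have 82% power to detect a difference of 5 points in change scores" comes from a two-group change-score calculation that does not use the mixed-model covariance, and it reproduces. A 6-month SD above 8.2 would lower power (75.9% at an SD of 9.0, normal approximation), but that would follow from the planning SD and not from the random intercept. Point estimates are essentially unaffected.

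**What to change.** In section 13.2, and in the FSFI domain and Aim 2a models that follow it:

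- Replace the random intercept with an unstructured 3x3 within-person covariance over T2 to T4.
- Name heterogeneous compound symmetry as the fallback if the model does not converge.
- State a small-sample degrees-of-freedom method that can be combined with pooling across the MICE imputations, and make sure the imputation model also allows a separate variance at each time point.
- A baseline-by-time term is optional. A single baseline slope does not bias the randomised comparison.

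The cost is wording in the analysis plan and four extra variance parameters (six for an unstructured 3x3 matrix against two for compound symmetry). With 92 to 120 patients the loss of precision is negligible. In the simulations this covariance kept the 6-month type I error between 4.4% and 5.1% in every scenario run.
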